3.1.7. Per-Protocol Set

The Per-Protocol Set (PPS) and Per-Protocol Set for Incontinence (PPS-I) exclude patients from the FAS and FAS-I due to important deviations from the protocol that may substantially affect the results of the efficacy endpoints (i.e., Major PDs associated with efficacy). The Per-Protocol set for Urodynamics (PPS-UES) exclude subjects from UES due to important deviations from the protocol that may substantially affect the results of the urodynamics endpoints. A supportive analysis using the PPS and PPS-I will be performed for the co-primary and secondary efficacy endpoints, and a supportive analysis using the PPS-UES will be performed for the primary urodynamics parameters (Qmax and PdetQmax). The final determination on protocol deviations, and thereby the composition of the Per-Protocol Sets, will be made prior to the unblinding of the database and will be documented per the Protocol Deviation Plan during the blinded data review

meeting. Subjects will be included in the treatment group to which they are randomized, regardless of which treatment was actually received, for the analyses of efficacy data using the PPS and PPS-I.

3.2. Violations and Deviation

Subjects who do not meet eligibility criteria but are still randomized will be analyzed according to the analysis sets described in Section 3.1.

Major protocol deviations are considered to have major impact on subject safety, efficacy or the validity of the study data.

Patients with major efficacy protocol deviations will be excluded from the PPS and PPS-I under the assumption that the deviation may have an impact on the efficacy analysis, and from PPS-UES under the assumption that the deviation may have an impact on the urodynamics analysis. This may include, but is not limited to the following:

- Subjects who do not meet the following inclusion criteria:
 - On a stable dose of alpha blocker
 - Average frequency of ≥ 8 and ≤ 20 micturitions per day in the baseline diary
 - Average frequency of ≥ 3 urgency episodes per day in the baseline diary
 - Average frequency of ≥ 2 nocturia episodes per night in the baseline diary
- Subjects who meet any of the following exclusion criteria:
 - Total 24-hour urine volume output of >3000 mL based on any baseline diary day
 - History of prostate surgery
 - Subject started using diuretics within 28 days prior to screening
 - Nocturnal Polyuria ($> 1/3$ of total urine output per 24 hours occurring at nighttime) assessed on any day of the baseline diary
 - Has received an intravesical or intraprostatic treatment with any botulinum toxin, resiniferatoxin, or capsaicin within 6 months prior to screening
 - Use of any prohibited anticholinergics or beta-3 adrenergic agonists as detailed in protocol section 10.6 within 28 days prior to screening
- Concomitant use of prohibited medications as detailed in protocol section 10.6
- $<70\%$ Investigational Product [IP] compliance from Baseline through Week 12
- Visit delay at or prior to Week 12 causing more than 14 days without IP
- Failed to complete any diary day for an expected Week 12 diary within Study Day 68-102 [PPS and PPS-I only]

Exclusion from per-protocol analysis is noted for each protocol deviation in the Protocol Deviation specifications.

The final list of major protocol deviations will be finalized and documented before database lock except for the deviation of wrong treatment which will be confirmed upon study unblinding. All major protocol deviations related to efficacy will be finalized prior to unblinding. Only major protocol deviations will be summarized and listed in the Clinical Study Report (CSR).

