25. Subjects who have systolic blood pressures ≥ 160 mmHg but < 180 mmHg are excluded, unless deemed by the investigator as safe to proceed in this study and able to complete the study per protocol; All subjects taking anti-hypertensives must be on stable doses for at least 3 months prior to the Screening Visit.
26. All subjects with signs and symptoms of uncontrolled hypertension, regardless of blood pressure measurement, are excluded from the study. These include, but are not limited to neurological symptoms or findings, hematuria, proteinuria, retinopathy, unstable angina, and acute heart failure.
27. Has a history of cerebral vascular accident, transient ischemic attack, unstable angina, myocardial infarction, coronary artery interventions (eg, coronary artery bypass grafting or percutaneous coronary interventions [eg, angioplasty, stent insertion]), or neurovascular interventions (eg, carotid artery stenting) within 6 months prior to the Screening Visit.

Subjects with these conditions should be on stable medical therapy for at least 3 months prior to the Screening Visit.

28. Has a history of injury, surgery, or neurodegenerative diseases (eg, multiple sclerosis, Parkinson's) that could affect the lower urinary tract or its nerve supply.
29. Has hematuria that was not evaluated, including microscopic hematuria (> 5 RBCs/hpf). Subjects with known, fully evaluated, benign hematuria may participate. Documentation must be obtained indicating an unremarkable upper urinary tract (kidneys and ureters) imaging study (eg, computerized tomography [CT] scan with and without contrast, renal ultrasound, magnetic resonance imaging [MRI], intravenous pyelogram, etc.) and cystoscopy. Subjects whose hematuria has not been previously evaluated may not be enrolled.
30. Has alanine aminotransferase or aspartate aminotransferase > 2.0 times the upper limit of normal (ULN), or bilirubin (total bilirubin) $> 1.5 \times$ ULN (or $> 2.0 \times$ ULN if secondary to Gilbert syndrome or pattern consistent with Gilbert syndrome).
31. Has an estimated glomerular filtration rate (eGFR) < 30 mL/min/1.73 m².
32. Use of any prohibited medications as detailed in [Section 6.5.1](#) (suitable washout periods from these medications are also described therein).
33. Had changed the dose of any medications listed in [Section 6.5.2](#) within 28 days prior to the Screening Visit or plans to initiate or change the dosing of any of these medications during the study.

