8.1.3. Screening

All screening evaluations must be completed and reviewed to confirm that potential subjects meet all eligibility criteria. The investigator will maintain a screening log to record details of all subjects screened and to confirm eligibility or record reasons for screening failure, as applicable. Inclusion and exclusion criteria ([Section 5.1](#) and [Section 5.2](#)) will be reviewed by the investigator or qualified designee at Screening, the start of the Run-in Period, and the start of the double-blind Treatment Period.

Subjects who fail to meet entry criteria may be rescreened **once**. (See [Section 8.1.2](#) regarding assignment of subject number.)

The Screening period may also be used for washout of prohibited medications (see [Section 6.5.1](#)).

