10.6. Appendix 6: Prohibited Medications and Non-Drug Therapies

The following medications are prohibited, as outlined in [Section 6.5.1](#).

Prohibited Medications Class	Examples	Washout Period/Comments
Anticholinergics	darifenacin, fesoterodine, hyoscyamine, oxybutynin, propantheline, solifenacin, tolterodine, and trospium	Subject must discontinue use at least 28 days prior to beginning completion of the Screening Bladder Diary and remain off this therapy during the study. If an anticholinergic/ antimuscarinic is used in an inhaler on a PRN/ as needed basis for the treatment of chronic obstructive pulmonary disease, it will be permitted.
Smooth muscle relaxants	flavoxate, dicyclomine, propiverine	Subject must discontinue use at least 28 days prior to beginning completion of the Screening Bladder Diary and remain off this therapy during the study
Beta-2 adrenergic agonists used for the treatment of stress urinary incontinence	clenbuterol	Subject must discontinue use at least 28 days prior to beginning completion of the Screening Bladder Diary and remain off this therapy during the study
Systemic beta-2 adrenergic agonist	terbutaline	No washout period; subject must remain off this therapy during the study
Antidiuretic hormones	desmopressin	Subject must discontinue use at least 28 days prior to beginning completion of the Screening Bladder Diary and remain off this therapy during the study
Beta-3 adrenergic agonists	mirabegron	Subject must discontinue use at least 28 days prior to beginning completion of the Screening Bladder Diary and remain off this therapy during the study
New start of BPH medications	Alpha-Blockers, eg, alfuzosin, doxazosin, silodosin, tamsulosin, and terazosin 5-ARI, eg, alfuzosin, dutasteride, and finasteride PDE5 inhibitors, eg, tadalafil	Subject must not start new use of these therapies during the study.
Intradetrusor or intraprostatic botulinum toxins	intradetrusor injection of botulinum toxin or intraprostatic injections	Subject must not have received an injection within 6 months prior to the Screening Visit and must not receive this therapy during the study
Any herbal medications to treat OAB symptoms, lower urinary tract symptoms of BPH or erectile dysfunction		Subject must not have received the herbal medications within 28 days prior to the Screening Visit and must not receive them during the study.
Diuretics		Subject must not start new diuretics during the study.

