3.1.2. Placebo Run-in Set

The Placebo Run-In Set consists of all subjects who receive placebo run-in treatment. Subjects will be considered run-in failures if they receive run-in treatment but are not randomized to receive double-blind medication. Subjects who inadvertently received vibegron during run-in are not included in the placebo run-in set.

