5.6.2. Concomitant Medication

Concomitant medications will be defined as medications started on or after the first dose of double-blind medication but prior to the last dose of the double-blind medication + 5 days, or started prior to double-blind medication and ongoing during the double-blind period. Post medication is the medication taken after the last dose of double-blind medication + 5 days (See Table 2). Partial medication start dates will be imputed as detailed in 4.2.3.

Non-OAB and OAB concomitant medications will be summarized separately.

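### SAP 3.2 counts the 28-day look-back for prohibited OAB drugs from screening, but protocol 10.6 counts it from the Screening diary, so men who met the washout are classed as per-protocol deviators

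*SAP*

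**What the plan says.** SAP 3.2 lists major efficacy deviations that take a man out of PPS and PPS-I, and out of PPS-UES where the urodynamics analysis is concerned. Under the exclusion criteria it names "Use of any prohibited anticholinergics or beta-3 adrenergic agonists as detailed in protocol section 10.6 within 28 days prior to screening". A later bullet adds concomitant use of prohibited medications, again citing protocol 10.6.

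For both drug classes protocol 10.6 reads: "Subject must discontinue use at least 28 days prior to beginning completion of the Screening Bladder Diary and remain off this therapy during the study". Protocol 8.1.3 adds: "The Screening period may also be used for washout of prohibited medications". The matching eligibility rule is Exclusion Criterion 32, which sends the reader to the prohibited-drug section and notes that "suitable washout periods from these medications are also described therein".

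The protocol does use the Screening Visit as anchor for other classes. For herbal products, 10.6 says "Subject must not have received the herbal medications within 28 days prior to the Screening Visit". The diary anchor for anticholinergics and beta-3 agonists is therefore a separate rule, not a loose way of saying Screening.

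Two further SAP statements matter. Section 5.6.2 says "Concomitant medications will be defined as medications started on or after the first dose of double-blind medication", or those begun earlier and still running in the double-blind period. Section 3.1.2 says "Subjects who inadvertently received vibegron during run-in are not included in the placebo run-in set".

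**The concern.** The SAP bullet cites the protocol rule but moves its starting point. Screening comes before the Screening diary, so counting back from Screening reaches further into the past than the protocol does. A man can satisfy the protocol in full and still be a major efficacy deviator under the SAP.

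The look-back also ends at Screening. Drug taken only between Screening and Day 1 is not covered by this bullet, although the baseline diary is filled in during run-in (SAP Table 3: first run-in dose to Day -1).

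At stake is the make-up of the per-protocol sets. SAP 3.1.7 uses PPS and PPS-I to support the co-primary and secondary endpoints, and PPS-UES to support Qmax and PdetQmax. SAP 6.1.2 repeats the co-primary MMRM on the PPS and also runs the multiply imputed ANCOVA on it. The version history shows that SAP 2.0 revised the per-protocol exclusions, so this wording is current.

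**Working it through.** No stated sample size, power or alpha depends on this rule, so the check is a count along the day-line.

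Inputs:
- Screening on day S, between Day -49 and Day -14; Run-in on day R, Day -14 ± 4 (protocol 10.7.1 and 10.7.2).
- The Screening diary starts at least 3 days before Run-in (protocol Table 1), so its latest first day is D = R - 3.
- Protocol 10.6: last use is compliant if it falls on or before D - 28.
- SAP 3.2: any use from S - 28 to S - 1 removes the man.

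**Compliant men who are removed.** Last-use days from S - 28 to D - 28 comply with the protocol. A man with such a last-use day who took the drug before Screening is caught by the SAP. The number of such days is (D - 28) - (S - 28) + 1 = D - S + 1. At the latest permitted diary start:

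| S | R | D = R - 3 | Latest compliant last use, D - 28 | Relative to Screening | Days, D - S + 1 |
|---|---|---|---|---|---|
| -49 | -14 | -17 | -45 | 4 days after | 33 |
| -49 | -10 | -13 | -41 | 8 days after | 37 |
| -42 | -14 | -17 | -45 | 3 days before | 26 |
| -35 | -14 | -17 | -45 | 10 days before | 19 |
| -21 | -14 | -17 | -45 | 24 days before | 5 |

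An earlier diary gives fewer days. Example: Screening on Day -49, last mirabegron dose on Day -50, diary from Day -20. The gap is 30 days, so the washout is met, yet the dose lies 1 day before Screening and the SAP removes him.

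Stopping at or after Screening is compliant only if D - 28 ≥ S. With D = R - 3 this means R - S ≥ 31 days, which the 35-day window (Day -49 to Day -14) allows.

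**Use that is missed.** Take pre-Screening use that breaks the protocol washout, so last use is after D - 28. Because D is never earlier than S, that day is also after S - 28, and the SAP bullet catches it. A man who continues his drug into Screening is caught too. What escapes is use that starts or resumes on or after Screening, with none in the 28 days before. If it stops before the first double-blind dose, it is also outside concomitant use under SAP 5.6.2. The uncovered span, S to Day -1, is 49 days for S = -49 and 21 days for S = -21.

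The baseline diary starts 3 to 7 days before Baseline (protocol Table 1). For a diary starting on Day -7, a stop day b leaves fewer than 28 days if -7 - b < 28, that is Day -34 to Day -1: 34 days. For a start on Day -3 it is Day -30 to Day -1: 30 days. Both counts hold for S at Day -35 or earlier; for S = -21 all 21 days qualify.

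**Precision, as context.** With power = Φ(δ / (σ√(2/n)) - 1.96) and 462 per arm, micturitions (0.46, SD 1.972) give 94.4% against a stated 94.3%, and urgency (0.60, SD 2.811) gives 90.0% against about 90%. The documents give no removal rate. If 2%, 5% or 10% of evaluable men left the PPS (assumption), power in that supportive analysis would be 93.9%, 93.3% or 92.0% for micturitions and 89.5%, 88.5% or 86.8% for urgency.

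**The case against.** The strongest reply is that the bullet sits under exclusion criteria and cites 10.6. A man who met the 10.6 washout does not meet Exclusion Criterion 32, and SAP 3.1.7 removes men only for important deviations from the protocol. The list in 3.2 is illustrative, the working flags are in the Protocol Deviation specifications (not among the documents reviewed), and membership is settled at a blinded data review. All this is true, so actual removals cannot be known from the plan. It does not repair the bullet: an open list can add exclusions, but it does not correct a stated anchor that differs from the section it cites.

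The gap after Screening is also open to debate. Protocol 8.1.6 records concomitant medication from consent onward, and on that wider meaning the next SAP bullet would cover it. An SAP term would normally carry the SAP's own definition; two possible readings are reason enough to settle it.

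A reader might infer more than the documents support:
- That the rule lets through men who simply stayed on their drug. It does not; they are caught.
- That many men are affected. No washout rate is given, and the protocol describes Screening as about 1 to 4 weeks, so a complete washout inside Screening fits only near the early edge of the window.
- That men given vibegron in run-in distort the results or are selected for weak response. SAP 3.1.2 does not say that any were randomized, and no exposure time is given. Keeping such a man in the FAS follows its intention-to-treat basis. Prior vibegron exposure already breaches Exclusion Criterion 36, and SAP 3.2 mentions a wrong-treatment deviation, without saying whether it reaches back to run-in.

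**Conclusion.** The anchor in SAP 3.2 contradicts protocol 10.6 and 8.1.3. On the literal text it turns compliant men into major efficacy deviators and removes them from PPS, PPS-I and PPS-UES. The narrower gap between Screening and Day 1 is real if concomitant use has its SAP 5.6.2 meaning.

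The consequence is limited. A reader might infer that the primary result is at risk. It is not: primary inference rests on the FAS, and N, power and alpha are unchanged. The SAP also plans multiply imputed ANCOVA on the FAS with a tipping-point analysis, so the PPS is not the only robustness check. Use before Day 1 is settled before treatment starts, so removing these men should not by itself favour one arm; it narrows the population to men without recent OAB drug use and costs some precision.

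The finding rests on reading screening as the Screening Visit or start of Screening, and on counting a last dose exactly 28 days before the diary as compliant. The number of men affected is unknown.

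**What to change.** In SAP 3.2 and the Protocol Deviation specifications, replace the 28-days-before-screening wording with use from 28 days before the first day of the Screening Bladder Diary through Day -1. State the boundary day: under 10.6 a last dose exactly 28 days before the diary is compliant, so it should not be flagged. This removes the over-exclusion by construction and closes the gap before Day 1. It changes only the analysis rule, not the washout.

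As a minor clarification, state that vibegron received in run-in is a per-protocol exclusion for any such man who was randomized.

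The cost is one amended line and one added line before unblinding. Concomitant medication dates are already recorded on the eCRF (protocol 6.5), and no participant is affected.

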4. GENERAL STATISTICAL CONSIDERATIONS

4.1. General Principles for Data Analysis

4.1.1. Multicenter Study

In this study the stratified permuted block randomization is not done within centers. The analyses will be conducted by pooling data from all study centers and will not include study center as a covariate in the statistical modeling.

4.1.2. Testing Strategy and Multiplicity Adjustments

A hierarchical gate-keeping procedure will be used to control the overall family-wise Type-I error rate at 2-sided $\alpha=0.05$ level over the co-primary and key secondary hypotheses stated in Section 1.2.3.

If statistical significance for both co-primary efficacy endpoints is achieved (i.e., if two-sided p-value for each endpoint is less than 0.05), then the secondary efficacy endpoints will be tested sequentially in the pre-defined order below.

1. Average number of nocturia episodes per night
2. Average number of daily urge urinary incontinence episodes for subjects with urinary incontinence at baseline
3. IPSS Storage score (1-week recall)
4. Average volume voided per micturition

Once a secondary efficacy endpoint is found to be insignificant (i.e., two-sided p-value ≥ 0.05), the testing procedure will stop. For all subsequent secondary efficacy endpoints, nominal p-values will be provided but will not be considered a formal test of the hypotheses. Unless otherwise stated, all statistical tests will be conducted at the 2-sided $\alpha=0.05$ level of significance.

All other additional and exploratory efficacy endpoints will be considered supportive and no multiplicity adjustments will be performed for these other efficacy endpoints. Nominal p-values will be computed for other efficacy endpoints as a measure of the strength of the treatment effect rather than formal tests of hypotheses, if applicable.

All confidence intervals will be 2-sided 95% confidence intervals, unless stated otherwise.

4.1.3. Examination of Subgroups

To determine whether the treatment effect is consistent across various subgroups, the co-primary endpoints will be summarized descriptively for each of the following subgroups:

- Alpha blocker use with or without 5-ARI (with vs. without)
- Baseline urinary incontinence (yes vs. no)
- Region (US vs. Non-US)

- Age category 1 (<55, ≥ 55 to <65, ≥ 65 to < 75, ≥ 75 years)
- Age category 2 (<65, ≥ 65 years)
- Age category 3 (<65, ≥ 65 to <75, ≥ 75 to <85, ≥ 85 years)
- Race (White, Black or African American, Asian and Other)
- Prior anticholinergic use (yes vs. no)
- Prior beta-3 agonist use (yes vs. no)

If any single subgroup constitutes <5% of total subjects, categories may be combined.

4.2. General Data Handling Conventions

4.2.1. Study Treatment Description

Randomized treatment groups will be displayed as shown in the following table:

Data Displays for Reporting	
Description	Order in TLF
Placebo	1
Vibegron 75mg	2
Overall (Demographic and baseline data)	3

4.2.2. Reporting Conventions

General rules

In general, all collected safety data and any derived efficacy and patient reported outcome (PRO) data will be presented in subject data listings for all enrolled subjects. Listings will be ordered by treatment group, subject number, and assessment week or event date. The treatment group presented in listings will be based on the planned assignment, unless otherwise noted.

Summary tables will be provided for all randomized subjects. Unless otherwise specified, all demographic and baseline data will be presented by treatment arm and overall. Efficacy, PRO and safety data will be presented by treatment arm. In general, continuous variables will be summarized to indicate the population sample size (N), number of subjects with available data (n), arithmetic mean, SD, median, minimum, Q1, Q3 and maximum values. Categorical variables will be summarized by the population size (N), number of subjects with available data (n), number of subjects in each category, and the percentage of subjects in each category. Unless otherwise noted, the denominator to determine the percentage of subjects in each category will be based on the number of subjects with available data (n) in the analysis set of interest. Select ordinal data may be summarized using both descriptive statistics and counts and percentages of subjects in each category, as appropriate.

For selected continuous safety endpoints, least squares means and 95% CIs will be derived from an analysis of covariance (ANCOVA) model with restricted maximum likelihood estimation. All models will include the baseline value of the parameter and any additional covariates will be noted; separate models will be fit for each timepoint. Example SAS code of a change from baseline at Week 12 is provided below:

```
proc mixed data = datain method = reml;
  class TRTA;
  model CHG = TRTA BASE / solution;
  where avisit = "Week 12";
  lsmeans TRTA / pdiff cl alpha=0.05;
run;
```

In the above code, CHG represents change from baseline, TRTA is the actual treatment received, and BASE is baseline value of the parameter.

The data analyses will be conducted using the SAS® System (SAS Institute Inc., Cary, NC) version 9.4 or above. The eClinical Solutions standard operating procedures will be followed for the creation and validation of all SAS programs and outputs.

Formats

Numeric data will be reported at the precision collected on the eCRF. The reported precision from non eCRF sources may be adjusted to a clinically interpretable number or decimal places. P-values will be reported to 4 decimal places, with p-values less than 0.0001 noted as <0.0001.

Unscheduled Visits

All visits, including unscheduled visits will be assigned to an analysis study visit using the all-inclusive windows defined in Section 4.2.4. However, data summaries will only report the visit nearest to the planned assessment time points for each parameter if multiple visits are within the analysis visit window, according to the Time and Events table. Assessments at unscheduled visits will be included for “any time On-treatment” timepoints and in data listings, as well as algorithms to determine the maximum or minimum.

